9.5. Interim Analysis

The SAP will describe the planned IA in greater detail.

The IA will be performed at a predetermined analysis time point. This time point is defined when 24 laboratory -confirmed DENV infections (see Section 9.4.1, General Considerations) are detected between baseline and the last day of dosing in the primary study population as defined in Section 9.3, Populations for Analysis Sets.

The IA will be performed by an independent statistical support group and will be reviewed by the IDMC who will receive unblinded safety and efficacy data (see Section 10.6.6, Committees Structure). After the review, the IDMC will make recommendations to the Sponsor Committee regarding the continuation of the study (see below for details). A Sponsor Committee, consisting of senior sponsor personnel not involved in the conduct of the study, will be established and will be responsible for decision making, considering the IDMC recommendation. An IDMC charter will be prepared before start of the study with more details on the IDMC and Sponsor Committee composition and organization.

Unblinded exposure response analyses will be performed by independent sponsor pharmacometricians using data available based on a predefined snapshot date at the IA, with adequate firewalls so the study team will remain blinded.

The aim of the IA at the end of Stage 1 is to assess PoC of the HDR and LDR for the primary objective. In this analysis, PoC is defined as a statistically significant reduction in the number of laboratory-confirmed DENV infections on active prophylactic dosing compared with placebo at the 20% one-sided significance level. The HDR and LDR will be tested hierarchically: First the HDR will be tested and if PoC is reached for the HDR, the LDR will be tested. Based on these results, the IDMC can advise to:

- Stop the study for futility, or
- Drop the LDR and continue the study with the placebo regimen and the HDR, or
- Continue the study with both active intervention groups (HDR and LDR) and placebo.

If the study continues, the IDMC may advise to open study recruitment to adolescent HHCs via protocol amendment.

The IDMC advice will be based on the following decision rule:

- If PoC is not reached for the HDR, the IDMC can advise to stop the study.
- If PoC is reached for the HDR but not for the LDR, the IDMC can advise to continue the study with only the HDR and placebo regimen and drop the LDR from the study.
- If PoC is reached for both HDR and LDR, the IDMC can advise to continue the study with both active intervention groups and placebo.

However, this rule is non-binding and based on a full review of all safety, efficacy, and exposure -response data available for the current study. In addition, data from other studies (eg, human challenge) may be available to guide the decision.

As the study design only allows for futility assessment at the IA, no multiplicity correction will be performed for the IA. In addition, the impact of potentially dropping the LDR at the IA on the comparison of the HDR with the placebo regimen at the FA was assessed through analytical derivation of the Type I error rate. This analysis showed the Type I error was well controlled (Type I error rate <2.5%).

10. SUPPORTING DOCUMENTATION AND OPERATIONAL CONSIDERATIONS

10.1. Appendix 1: Abbreviations

ABV alcohol-by-volume AE adverse event

AIH autoimmune hepatitis
ALP alkaline phosphatase
ALT alanine aminotransferase

APTT activated partial thromboplastin time

AST aspartate aminotransferase BCRP breast cancer resistance protein

BMI body mass index BUN blood urea nitrogen

CFR Code of Federal Regulations

CI confidence interval COVID-19 Coronavirus Disease 2019 CPK creatine (phospho)kinase

CRF case report form CV coefficient of variation

CYD-TDV chimeric yellow fever – dengue virus tetravalent dengue vaccine

CYP cytochrome P450

DAIDS Division of Acquired Immunodeficiency Syndrome

DENV dengue virus

DHF dengue hemorrhagic fever

DMID Division of Microbiology and Infectious Diseases

DNA deoxyribonucleic acid DSS dengue shock syndrome EC₅₀ 50% effective concentration

ECG electrocardiogram eDC electronic Data Capture

eGFP enhanced green fluorescent protein ELISA enzyme-linked immunosorbent assay

FA final analysis

FC crystallizable fragment FDA Food and Drug Administration

FIH first-in-human

GCP Good Clinical Practice GGT gamma-glutamyltransferase GLDH glutamate dehydrogenase

HCC health care center HCP health care provider

HDR high-dose JNJ-64281802 regimen

HHC household contact

HRT hormonal replacement therapy

IA interim analysis
IB Investigator's Brochure
IC₅₀ 50% inhibitory concentration
ICF informed consent(/assent) form

ICH International Council for Harmonisation of Technical Requirements for Pharmaceuticals for

Human Use

ICMJE International Committee of Medical Journal Editors

IDMC Independent Data Monitoring Committee

IEC Independent Ethics Committee

Ig immunoglobulin

IMP investigational medicinal product

INR international normalized ratio IRB Institutional Review Board

IUD intrauterine device

IUS intrauterine hormone-releasing system interactive web response system **IWRS** lactational amenorrhea method LAM

LC-MS/MS liquid chromatography-mass spectrometry/mass spectrometry

LD loading dose

LDH lactate dehydrogenase

low-dose JNJ-64281802 regimen LDR

low density lipoprotein LDL

lower limit of laboratory normal range LLN

maintenance dose MD

MDR1 multidrug resistance protein 1

Medical Dictionary for Regulatory Activities MedDRA

neutralizing antibody nAb

no observed adverse effect level **NOAEL**

NS nonstructural protein

nonsteroidal anti-inflammatory drug **NSAID** protocol clarification communication **PCC**

polymerase chain reaction **PCR** polyethylene glycol 400 PEG400 PΙ principal investigator PK pharmacokinetic(s) proof-of-concept PoC

POC product quality complaint

PT prothrombin time

partial thromboplastin time PTT QT corrected for heart rate QTc

QT corrected for heart rate according to Bazett's formula OTcB QT corrected for heart rate according to Fridericia's formula **OTcF**

RBC red blood cell ribonucleic acid **RNA**

RT-qPCR quantitative reverse transcription polymerase chain reaction

SAE serious adverse event SAP Statistical Analysis Plan SD standard deviation

SUSAR suspected unexpected serious adverse reaction

table of content TOC

uridine diphosphate-glucuronosyltransferase **UGT** ULN upper limit of laboratory normal range

United States US

United States of America USA USP United States Pharmacopeia

viral kinetic model VKM **WBC** white blood cell

WHO World Health Organization

VLviral load

Definitions of Terms

area under the plasma concentration-time curve from 0 to 24 hours AUC_{0-24h} $AUC_{0-\infty}$ area under the plasma concentration-time curve from 0 hours to infinity

 AUC_{τ} area under the concentration curve during one dosing interval

 C_{max} maximum plasma concentration C_{trough} observed analyte concentration just prior to the beginning or at the end of a dosing interval

 $t_{1/2}$ elimination half-life

 t_{max} time to maximum concentration

10.2. Appendix 2: Rash Management

Dengue symptomatic infection is known to result in skin rashes in most patients. Rashes may potentially also be related to the study intervention, and it may not be possible to differentiate between a rash secondary to DENV infection and one related to the study intervention. In all cases of rash that are not related to DENV infection, the below rash management should be followed.

In case a causal relationship between the rash and the study intervention cannot be excluded, then the following visits and assessments will be performed as indicated. Unscheduled follow-up visits for close follow-up of rash will be performed based on the grade (severity) of the rash. At the investigator's discretion, additional visits and assessments can be performed.

If a causal relationship between the rash and the study intervention cannot be excluded, safety blood samples need to be taken during the (unscheduled) visits as described below. The following parameters need to be tested: aspartate aminotransferase (AST), ALT, creatinine, erythrocyte sedimentation rate, and a complete blood cell count (including hemoglobin, hematocrit, red blood cell [RBC] count, white blood cell [WBC] count, neutrophils, lymphocytes, monocytes, eosinophils, basophils, and platelet count).

The rash event should be captured in the Adverse Event Section of the CRF, and in more detail in the specific rash assessment pages of the CRF.

Participants should be informed that they should contact the investigator and visit the study site immediately (unscheduled visit, Day 0 of the rash) when they notice any rash. The skin reaction should be evaluated at the study site the same day (if possible) or the next day. Participants should be advised to contact the investigator immediately if there is any worsening of the rash, if any systemic signs or symptoms appear, or if mucosal involvement develops.

Grading of rash events will be based on the Division of Acquired Immunodeficiency Syndrome (DAIDS) Table for Grading the Severity of Adult and Pediatric Adverse Events (DAIDS 2017).

Monitoring of the evolution of rash events will be performed as described in Table 5 below.

 Table 5:
 Management of Rash Events by Severity Grade

Status: Approved, Date: 19 July 2023

			•	
	Definition	Study	Activities by Day ^a	Referral to Dermatologist
		Intervention		and Dermatology
		Action		Activities
Grade 1 rash ^b	Localized rash that is easily tolerated	Study intervention intake may be	Day 0 : Required on-site unscheduled visit for initial rash evaluation, if participant is outside the study site.	Not required
	and/or may require	continued at the	Safety laboratory assessments are required.	
	one dose of medication.	investigator's discretion.	• Digital pictures ^d should be taken (preferred within 24 hours) after the onset of the rash.	
			 Cetirizine, levocetirizine, topical corticosteroids, or antipruritic agents may be prescribed. 	
			Day 1 and 7 : Safety blood samples and digital pictures ^d should be taken.	
			After Day 7: If the rash is unresolved, additional unscheduled visits can be	
			performed at the investigator's discretion.	
			In case the rash evolves from a Grade 1 to a higher grade, additional	
			unscheduled visits have to be conducted according to the guidelines for	
			Grade 2 or Grade 3-4 rash, respectively.	
			Upon resolution/stabilization of the rash: Digital pictures ^d should be taken and	
			the final rash assessment pages of the CRF should be completed.	

Def	efinition	Study Intervention Action	Activities by Day ^a	Referral to Dermatologist and Dermatology Activities
rash ^b mad or t Syn (pai doe with requone	iffuse, aculopapular rash, target lesions. ymptomatic pain/pruritus) but pes not interfere ith function and/or quires more than ne dose of edication.	Study intervention intake may be continued at the investigator's discretion	 Day 0: Required on-site unscheduled visit for initial rash evaluation, if participant is outside the study site. Safety laboratory assessments are required. Digital pictures^d of skin lesions should be taken (preferred within 24 hours) after the onset of the rash. Cetirizine, levocetirizine, topical corticosteroids, or antipruritic agents may be prescribed. Day 1 and 7: Safety blood samples and digital pictures^d should be taken. After Day 7: If the rash is unresolved: If there is an increase in AST/ALT of ≥2 times the ULN, participants should be followed weekly (or more frequently, at the investigator's discretion) with repeated local laboratory assessments and digital pictures^d until resolution of the AST/ALT abnormalities. If there is no increase in AST/ALT, additional unscheduled visits (including local laboratory assessments and digital pictures^d) can be performed at the investigator's discretion. If the rash evolves from a Grade 2 to a Grade 3-4 rash, additional unscheduled visits have to be conducted according to the guidelines for Grade 3-4 rash. Upon resolution/stabilization of the rash: Digital pictures^d should be taken and the final rash assessment pages of the CRF should be completed 	Not required

	Definition	Study Intervention Action	Activities by Day ^a	Referral to Dermatologist and Dermatology Activities
Grade 3	Diffuse rash AND vesicles or limited	Must permanently	Day 0 : Required on-site unscheduled visit for initial rash evaluation, if participant is outside the study site.	Required ^c
	number of bullae or	discontinue and		Biopsy required within
	superficial	be withdrawn	Day 0 and 1 :	24 hours after onset of
	ulcerations of	from the study;	 Safety laboratory assessments are required. 	rash.
	mucous membrane	no rechallenge	• Digital pictures ^d of skin lesions should be taken within 24 hours after	
	limited to 1 site, OR	allowed.	the onset of the rash and on Day 1.	
	elevations in AST/ALT >2x ULN,		Further visit(s) : Appropriate management and follow-up required until resolution of rash or until clinical stability is reached.	
	OR oral body		Days 2, 3, and 4 : Only if the participant's AST/ALT on Day 0 and/or Day 1 of rash >2x ULN and/or in case of rash progression:	
	temperature		 Additional safety blood samples are required. 	
	≥39.3°C to <40.0°C (≥102.7°F to		• Digital pictures ^d are to be taken.	
	<104.0°F),		Day 5 : Regardless of the Day 0/1 AST/ALT levels or rash progression:	
	OR		 Additional safety blood samples are required. 	
	eosinophils >1,000/mm ³ ,		• Digital pictures ^d are to be taken.	
	OR		After Day 5: Weekly follow-up visits are required (or more frequently at the	
	serum sickness-like		investigator's discretion) as long as Grade 3-4 rash is present. Once Grade 3-4	
	reaction.		rash has resolved to ≤Grade 2 rash, follow-up should be done according to the	
			instructions for follow-up visits for Grade 1 or Grade 2 rash, respectively.	
			 Only if the participant's AST/ALT on Day 5 of rash is still >2x ULN 	
			and/or in case of rash progression, additional safety blood samples and	
			digital pictures ^d are required at these weekly follow-up visits, until resolution or stabilization of the AST/ALT elevations.	
			Upon resolution/stabilization of the rash: Digital pictures ^d should be taken and the final rash assessment pages of the CRF should be completed.	

Status: Approved, Date: 19 July 2023

	Definition	Study Intervention Action	Activities by Day ^a	Referral to Dermatologist and Dermatology Activities
Grade 4 rash ^b	Potentially life-threatening rash with: Extensive or generalized bullous lesions, OR ulceration of mucous membrane involving 2 or more distinct mucosal sites, OR Stevens-Johnson syndrome, OR		 Day 0: Required on-site unscheduled visit for initial rash evaluation, if participant is outside the study site. Day 0 and 1: Safety laboratory assessments are required. Digital pictures^d of skin lesions should be taken within 24 hours after the onset of the rash and on Day 1. Further visit(s): Appropriate management and follow-up required until resolution of rash or until clinical stability is reached. Days 2, 3, and 4: Only if the participant's AST/ALT on Day 0 and/or Day 1 of rash >2x ULN and/or in case of rash progression: Additional safety blood samples are required. Digital pictures^d are to be taken. 	
	toxic epidermal necrolysis.		 Day 5: Regardless of the Day 0/1 AST/ALT levels or rash progression: Additional safety blood samples are required. Digital pictures^d are to be taken. After Day 5: Weekly follow-up visits are required (or more frequently at the investigator's discretion) as long as Grade 3-4 rash is present. Once Grade 3-4 rash has resolved to ≤Grade 2 rash, follow-up should be done according to the instructions for follow-up visits for Grade 1 or Grade 2 rash, respectively. Only if the participant's AST/ALT on Day 5 of rash is still >2x ULN and/or in case of rash progression additional safety blood samples and digital pictures^d are required at these weekly follow-up visits, until resolution or stabilization of the AST/ALT elevations. Upon resolution/stabilization of the rash: Digital pictures^d should be taken and the final rash assessment pages of the CRF should be completed. 	

Definition	Study	Activities by Day ^a	Referral to Dermatologist
	Intervention	•	and Dermatology
	Action		Activities

AE = adverse event; ALT = alanine aminotransferase; AST = aspartate aminotransferase; CRF = case report form; IDMC = Independent Data Monitoring Committee; ULN = upper limit of normal.

Notes:

Local laboratory assessments are to be used for rash management. A copy of the local laboratory reports should be de-identified and will be collected by the site manager.

[figure not shown]
A copy of the dermatologist's report, and biopsy if performed, should be made anonymous and will be collected by the site manager. Dermatologist fees for evaluating participants who experience a rash will be reimbursed by the sponsor.

Digital pictures will be de-identified and stored at the study site and on the sponsor's secure server. Only the sponsor team members and the IDMC members will have access to the sponsor's secure server.

Per investigator's discretion, the participant may be treated symptomatically until the rash resolves.

- a. Day 0 of the rash is the first day of investigator assessment and not the first day of rash as reported by the participant. The initial visit should be conducted as soon as possible after the participant contacts the investigator to report the AE (ie, preferably on Day 0). The initial visit and subsequent visits to manage the rash may require unscheduled visit(s).
- b. The participant should be advised to contact the investigator immediately if there is any worsening of the rash, if any systemic signs or symptoms appear, or if mucosal involvement develops. In case the rash evolves to a higher grade than that first observed, management of the rash should follow the guidelines indicated for the higher grade.
- c. If applicable, dermatologist visit should occur preferably within 24 hours after onset of rash.
- d. Digital pictures to be taken at the study site.

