- Elimination: In rats, elimination of JNJ-64281802 was almost completely via metabolism with low/negligible excretion in bile (approximately 3%) and urine (<0.001%).
- Pharmacokinetic (PK) drug interaction: In vitro, JNJ-64281802 did not induce CYP1A2 at 1 and 10 μ M, nor CYP3A4 at 1 μ M. At 10 μ M, JNJ-64281802 was shown to be a CYP3A4 inducer. JNJ-64281802 showed weak inhibition potential toward CYP1A2 and CYP2D6 (50% inhibitory concentration [IC₅₀] >30 μ M), and inhibition of CYP2C9 (IC₅₀ = 3.7 μ M), CYP2C8 (IC₅₀ = 7.4 μ M), and CYP2C19 (IC₅₀ = 10.3 μ M). Due to metabolic activation of CYP3A4/5-mediated metabolism of midazolam and CYP3A4-mediated metabolism of testosterone, no results were available for these CYP/probe substrate combinations, and time-dependent inhibition potential could not be assessed.

Clinical Studies

Study 64281802DNG1001

The Phase 1, double-blind, randomized, placebo-controlled, FIH study 64281802DNG1001 (EudraCT number: 2018-002201-62) examined the safety, tolerability, and PK of increasing single (in 39 participants) and multiple oral doses (in 47 participants) of JNJ-64281802 in healthy adult participants. An open-label, randomized, crossover, relative oral bioavailability part (in 36 participants) was included to study the PK and safety following 2 CCI formulation concepts compared with an oral solution, and to study the food effect on JNJ-64281802.

Safety

JNJ-64281802 was generally safe and well tolerated. No safety concerns were identified at single doses up to 1,200 mg and at multiple doses up to 560 mg once daily for 10 days or 400 mg once daily for 31 days. Two Grade 2 events of rash occurred in the multiple ascending dose part that were considered very likely related to JNJ-64281802 by the investigator. One Grade 2 rash occurred in a participant in the 10-day 560 mg JNJ-64281802 group on the last day of dosing (Day 10) and resolved after 35 days. The other Grade 2 rash occurred in a participant in the 31-day 400 mg JNJ-64281802 group on dosing Day 13 and resolved after 47 days. This participant completed the 31-day dosing period as planned.

Exposure-response analysis was based on time-matched QT interval corrected for heart rate (QTc). Holter data supports the absence of an effect of JNJ-64281802 on cardiac repolarization at the JNJ-64281802 concentration range investigated in Study DNG1001.

Human Pharmacokinetics

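### Protocol Table 5 gives two conflicting actions for a non-dengue diffuse rash, Grade 2 on skin findings and unresolved after rash Day 7, once AST/ALT exceeds 2x ULN

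*Protocol*

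**What the plan says.** Protocol Appendix 2 applies to rashes not related to DENV infection, and its Table 5 assigns actions by grade.

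- **Grade 2 row.** The definition covers a diffuse maculopapular rash or target lesions. On dosing: "Study intervention intake may be continued at the investigator's discretion". Dermatology referral is not required. Bloods are taken on rash Days 0, 1 and 7. For a rash unresolved after Day 7: "If there is an increase in AST/ALT of ≥2 times the ULN, participants should be followed weekly", with local laboratory tests and pictures until the enzyme abnormalities have resolved. The next bullet begins "If there is no increase in AST/ALT, additional unscheduled visits" and leaves those visits to the investigator.
- **Grade 3 row.** The definition opens with a diffuse rash combined with vesicles, limited bullae or mucosal ulceration at one site, and then adds a list joined by OR. One item is "elevations in AST/ALT >2x ULN". The actions are permanent discontinuation, withdrawal from the study, no rechallenge, dermatology referral, and a biopsy within 24 hours of rash onset.
- **Escalation.** The Grade 2 row adds: "If the rash evolves from a Grade 2 to a Grade 3-4 rash, additional unscheduled visits have to be conducted", following the Grade 3-4 guidance. Footnote b says of a rash that evolves to a higher grade: "management of the rash should follow the guidelines indicated for the higher grade".

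**The concern.** The same findings (diffuse rash, skin appearance unchanged at Grade 2, AST/ALT above 2x ULN) lead to two different instructions on whether the participant keeps taking study intervention. One site could monitor weekly and continue dosing. Another could stop, withdraw the participant and arrange a biopsy. Each could point to a row of Table 5.

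Rash is a listed potential risk of the drug in Protocol 2.3.1. A rash lasting beyond Day 7 is realistic: Protocol 2.2 describes two Grade 2 rashes in the Phase 1 study judged very likely drug-related. One began "on the last day of dosing (Day 10) and resolved after 35 days"; the other resolved after 47 days. What is at stake is consistent safety management across sites and the interpretation of discontinuations for rash.

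**Working it through.** The plan gives no figure to reproduce, so the check compares the two rows on the enzyme criterion and looks for any rule that decides between them.

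**Step 1: overlap.** Let x be AST/ALT as a multiple of ULN, for a diffuse rash unresolved after rash Day 7.

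| x | Grade 2 weekly bullet (x ≥ 2.0) | Grade 3 definition (x > 2.0) |
|---|---|---|
| raised, but below 2.0 | no | no |
| exactly 2.0 | yes | no |
| above 2.0 | yes | yes |

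Every x above 2.0 meets both texts. The first line shows a smaller gap: a raised value below 2.0 falls under neither the weekly bullet nor the bullet for no increase.

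**Step 2: does the reading of AND/OR matter?** The Grade 3 definition can be read as diffuse rash AND (vesicles OR enzymes OR ...), or as (diffuse rash AND vesicles) OR enzymes OR .... For a diffuse rash, both readings give Grade 3 once x exceeds 2.0. They differ only for target lesions that are not diffuse: under the first reading these stay Grade 2, and the weekly bullet properly applies to them.

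**Step 3: does another section decide?**
- Appendix 11 stopping and increased-monitoring criteria all start at 3x ULN or higher, so nothing there covers values above 2x and below 3x ULN.
- Appendix 9 calls AST or ALT up to 2.5x ULN a Grade 1 laboratory abnormality. Its own Grade 3 rash definition uses skin and mucosal findings only.

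Between 2x and 3x ULN, then, apart from general investigator judgement, the choice of Table 5 row decides whether dosing stops.

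**Step 4: how much dosing is in question?** By footnote a, rash Day 0 is the day of first investigator assessment; call it study day d. The first day after rash Day 7 is study day d + 8, and dosing ends on Day 28. Dosing days in question = 28 − (d + 8) + 1 = 21 − d. For d = 1 this is 20 days, for d = 20 it is 1 day, and for d = 21 it is 0. Dosing is at issue only for rashes first assessed on or before Day 20.

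**Step 5: can the Grade 3 row be applied as written this late?** The biopsy is due within 24 hours of rash onset. By rash Day 8 that limit has long passed. A participant moved to Grade 3 at that point cannot comply.

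**The case against.** The best defence is that Table 5 already resolves the overlap. If its definitions set the grade, a diffuse rash with AST/ALT above 2x ULN is Grade 3, and the escalation line and footnote b send it to the Grade 3 row. The Grade 2 bullet itself speaks of follow-up, not of continuing the drug. Much of this stands: it is the better reading, and it fixes the direction of the correction.

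It does not remove the conflict. Both rules turn on a rash that evolves, whereas the bullet expressly provides, within the Grade 2 row, for a participant whose enzymes are raised. The escalation line also mentions only visits. Appendix 2 bases rash grading on the DAIDS table, and the Appendix 9 definition of Grade 3 rash has no enzyme criterion, so a site grading from there would stay at Grade 2.

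A reader might go further and infer that the bullet is redundant because the Grade 3 row has its own weekly bloods. The documents do not support that. Those bloods are required only "if the participant's AST/ALT on Day 5 of rash is still >2x ULN" or if the rash progresses. The Grade 2 schedule has no Day 5 sample, so a participant whose enzymes first cross 2x ULN at Day 7 has no scheduled value to trigger them.

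Nor would deleting the bullet change required follow-up only at exactly 2.0x ULN. The bullet runs until the abnormality resolves, so a participant falling from 2.4x to 1.6x must still be seen weekly under it. The Grade 3 row allows its bloods to end at stabilisation.

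**Conclusion.** The inconsistency is real. For a non-dengue diffuse rash, Grade 2 on skin findings and unresolved after rash Day 7, Table 5 gives both a discretionary-dosing path and a mandatory-stop path for all AST/ALT values above 2x ULN. No other section clearly chooses between them below 3x ULN.

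It is minor. The number of participants affected is not given and may be zero. The SAP Introduction records that the study ended on 02 October 2024 for portfolio reasons, so correction can no longer alter dosing in this trial. No efficacy endpoint, power calculation or alpha is affected. The conclusion assumes that Table 5's own definitions are meant to govern rash management and that rash Day 0 is the first investigator assessment.

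Two stronger inferences should be avoided:

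- The Phase 1 count of 2 Grade 2 rashes among 47 multiple-dose participants does not estimate the affected group. AST/ALT for those cases is not given, and their doses (560 mg and 400 mg daily) exceeded the 150 mg or 50 mg maintenance doses here. They show only that such rashes can persist past Day 7.
- SAP 5.6.2 cites only Appendix 9 for toxicity grades. That is not a reporting error that changes results: the SAP tabulates the grades that investigators assigned and is read with the protocol, which points to Section 10.2 for rash. No count changes.

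**What to change.** In Table 5, Grade 2 row, After Day 7:

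1. Keep the weekly follow-up bullet and its endpoint, resolution of the enzyme abnormality.
2. Add: *A diffuse rash with AST/ALT >2x ULN at any time meets the Grade 3 definition: permanently discontinue study intervention and follow the Grade 3 row, and continue weekly local laboratory assessments until the AST/ALT abnormalities resolve.*
3. For a rash that becomes Grade 3 after onset, count the 24-hour biopsy limit from the time the Grade 3 definition is first met.
4. Leave target lesions that are not diffuse under the present bullet.
5. In the next bullet, replace the condition of no enzyme increase with: *AST/ALT has stayed <2x ULN throughout the rash*. This also closes the gap for raised values below 2x ULN and keeps weekly testing for a participant whose values have fallen back below the threshold.

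The cost is a few lines in one table and no new analysis. The small downside is that a few participants with modest enzyme rises would stop dosing, which the Grade 3 row already requires. With the study ended, the edit serves the record, the interpretation of any differing site decisions, and any later protocol that reuses the table.
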